9.2. Description of the Study Cohort

The study cohort will consist of 12 PCD subjects with mutations in genes associated with a mild pulmonary phenotype (RSPH1, RSPH9, RSPH4a, or DNAH11) and 12 PCD subjects with mutations in genes associated with a more severe pulmonary phenotype (DNAH5, DNAI1, CCDC39, or CCDC40). A subject with mild pulmonary phenotype will typically have later onset of respiratory symptoms, better lung function, and milder bronchiectasis [4]. The age of patients will range between 12-90 years old. Eight healthy patients will be enrolled and undergo the same MCC protocol to obtain data for comparison. All subjects following the protocol will be included in the database. Subjects not

completing the protocol will be replaced. Baseline measurements of population (age, gender, race, FEV1) will be tabulated, for the whole population and per group (mild genotype, severe genotype, healthy) using mean and standard deviation and frequencies with percentages as appropriate. Data will be plotted in graphical figures including as histograms, bar plots, and scatter plots.

9.3.Aim-Specific Plans

Aim 1: To estimate how MCC measurements vary in PCD subjects with mutations in genes that are associated with mild or severe disease, relative to healthy subjects, and compare the 3 populations in term of Average Clearance.

Aim 1 is measuring MCC in PCD subjects having confirmed mutations in genes associated with a milder clinical phenotype and subjects with PCD caused by mutations in genes associated with a more severe clinical phenotype. These measurements will be reported as estimates of the means and standard deviations of Ave60Clr for each group, with associated confidence intervals. The baseline MCC in PCD subjects with “mild genotypes” and “severe genotypes” will be compared to healthy subjects. Our expected result is that subjects with mutations in genes associated with mild disease will display lower MCC rates than healthy subjects, and subjects with mutations in genes associated with severe disease will be even lower. For this comparison, we will use an ANOVA followed by multiple comparisons, using the Tukey Kramer correction. Then, to control for other possible sources of variations, age, gender and the initial deposition C/P will be added as covariates to PCD groups in a linear regression model on MCC.

Aim 2: To characterize the effect of a short acting beta agonist (SABA) on MCC in PCD subjects with mutations in genes that are associated with mild or severe disease, and compare the 2 populations in terms of change in Average Clearance.

In aim 2, we will be measuring the effect of albuterol on MCC in PCD subjects. We will look at the change between Ave60Clear (before albuterol) and Ave120Clr (after albuterol) for each subject. Estimates of the means and standard deviations with associated confidence intervals will be reported for each group. Using paired t-tests, we will verify if the change is significantly different than 0. The difference between the 2 PCD groups will then be analyzed with an independent t-test. Age, gender and the initial deposition C/P will be added as covariates to PCD groups in a linear regression model on MCC.

As this is not a randomized crossover design nor a parallel-arm design, our proposed comparison pre- to post-albuterol is uncontrolled and cannot assess the efficacy of SABA. The goal of our study is to obtain first estimates of the immediate effect albuterol on MCC in a small, controlled population.

Aim 3: To characterize cough clearance in PCD subjects with mutations in genes that are associated with mild or severe disease, and compare the 2 populations in terms of change in Average Clearance.

We will compare cough clearance in PCD subjects with mutations associated with mild disease with PCD subjects with mutations in genes associated with more severe disease. Cough clearance will be measured as the change in retention between 120 and 150 min post deposition. This change between Ave120Clr and Ave150Clr will be tabulated for each PCD group in term of means and standard deviations with associated confidence intervals and compared to 0 using paired t-tests. The difference between the 2 PCD groups will then be analyzed with an independent t-test. Age, gender and the initial deposition C/P will be added as covariates to PCD groups in a linear regression model on MCC.

For all aims, all tests will be 2-sided, with $\alpha=0.05$. Tests with p values above 0.05 will be considered inconclusive.

Expected results, potential problems, and alternatives. We expect to observe a significant rate of MCC (different from 0) in the group of PCD patients with mutations in genes associated with a milder phenotype. Based on previous studies of ciliary activity in PCD subjects with mutations associated with a more severe phenotype, we expect to see little or no MCC in this group of PCD patients. Further, we expect the rate of MCC to be significantly greater in subjects in the “mild genotype” group compared to the PCD patients in the “severe genotype” group. We expect that subjects with a mild genotype will respond to albuterol with an increase in MCC while the PCD patients with the severe genotype will not. We expect that subjects with mutations in genes associated with a mild phenotype will have better cough clearance compared to subjects with mutations in genes associated with a severe phenotype. As we have performed many similar studies in the past, including studies of MCC in PCD subjects, we anticipate no technical difficulties in carrying out these studies. If there is no difference detected between the groups of PCD patients, this would suggest that the less severe clinical phenotype observed in some patients is not due to the maintenance of a low level of MCC. Nevertheless, this would be an important experimental finding, as it would indicate that some other mechanism is responsible for the difference in phenotype.

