4.1 Treatment Design

Type of Design: Open label; two group study with healthy controls

Screening/Baseline: Participants will undergo a general medical screening visit to include vital signs, physical exam and pregnancy test (if applicable), then proceed with spirometry.

Intervention/Treatment

Participants will inhale aerosolized radiolabeled sulfur colloid ($Tc99m$ -SC) and will undergo gamma scintigraphy to measure mucociliary and cough clearance (MCC/CC) of the radiolabeled particles from the airways in both groups. During the first hour of MCC imaging patients will attempt to avoid coughing. Patients will then inhale 4 puffs of albuterol (90 mcg/puff via metered dose inhaler (MDI) with spacer) to assess the effect of beta-adrenergic stimulation on MCC over the second hour of MCC

imaging. After the two hours of MCC imaging patients will perform spirometry and directed coughing over a 30 minute period during which CC will be measured, again by gamma scintigraphy. Subjects will then rest (app 3.5 hours) and be scanned for 15 minutes at 6 hour \pm 30 minutes post initial MCC/deposition scan.

Table of procedures

| PCD MCC/CC study flow sheet | minutes needed | cumulative min |
|---|----------------|----------------|
| 1 Vital signs, PE,pregnancy test, PFT | 30 | 30 |
| 2 Put Americium fiducial markers on | 5 | 35 |
| 2 Co57 Transmission scan | 5 | 40 |
| 3 Background scan | 15 | 55 |
| 4 Radioaerosol inhalation | 5 | 60 |
| 5 MCC scan (no cough) | 64 | 124 |
| 6 Albuterol MDI (4 puffs with spacer) | 6 | 130 |
| 7 MCC scan post albuterol | 54 | 184 |
| 8 PFT and directed coughing (30 coughs including any spontaneous induced by PFTs) | 20 | 204 |
| 9 CC scan post PFT/cough | 4 | 208 |
| 10 Rest until final scan 6 hours after beginning of #5 | 210 | 418 |
| 11 6 hour post initial radioaerosol MCC scan | 15 | 433 |

Unscheduled Visits: There is no expectation for unplanned visits. Subjects will simply be rescheduled if they have a change in health.

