6.7. Withdrawal / Discontinuation of Enrolled Participants

Patient's participation will be discontinued if:

1. Subject develops new or worsening respiratory symptoms including shortness of breath or decrease in FEV1 of 20% or greater.
2. Subject develops a condition that is an exclusion criterion.
3. Subject is noncompliant with the recommended withholding of SABA or ICS/LABA for 12 hours prior to study.

If any of the above are met, then patient will not continue.

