7.8. Premature Discontinuation

Study is considered completed after the last scan of the day. Subjects may withdraw at any time. Subjects may be withdrawn at any time for safety concerns. Subjects who have any unanticipated problems (UPs) with the study procedures will be monitored until resolution of the symptoms.

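### Sections 9.2, 7.8 and 9.5 together give a completers-only cohort, so valid clearance data can be displaced by a later event; analyse each aim on the measurements it needs

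*Combined protocol and SAP*

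**What the plan says.** Section 9.2 sets the cohort at 12 mild-genotype, 12 severe-genotype and 8 healthy subjects. It then states "All subjects following the protocol will be included in the database", and says that subjects not "completing the protocol will be replaced". Section 7.8 fixes the point of completion: "Study is considered completed after the last scan of the day". On the flow sheet in section 4.1 that scan is the 6-hour image, "6 hour post initial radioaerosol MCC scan | 15 | 433". Section 9.5 expects no withdrawals, but says that a subject who withdraws consent will be replaced so that the sample size wanted for analysis is reached. Section 9.6 allows for 20% dropout and gives no timing for it.

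The outcome scans come much earlier in the day. The flow sheet shows "MCC scan (no cough) | 64 | 124" for the baseline hour and "MCC scan post albuterol | 54 | 184" for the hour after albuterol, and the post-cough scan ends at minute 208. The regression models in section 9.3 adjust for age, gender and the initial central/peripheral ratio. Section 9.1 mentions 6-hour clearance only as a covariate that may be included.

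**The concern.** Completion is tied to the one scan that no stated outcome or section 9.3 model needs. A subject can supply a full primary measurement and then fail to complete, through a safety stop, a withdrawal or a missed 6-hour image, and under these sections is replaced.

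The protocol itself contains such a route. Spirometry is scheduled at baseline and again after albuterol (section 10.2), and the second session occupies minutes 184 to 204. A fall in FEV1 that meets the individual criterion in sections 6.7 and 10.5 would, as scheduled, be found only after the Aim 1 and Aim 2 scans are over. A 210-minute rest before the last scan follows.

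Two things are at stake: valid scans from subjects with rare genotypes go unused, and the cohort becomes selected if later stopping is related to clearance. Aim 1 is reported as means, standard deviations and confidence intervals, so who is included feeds directly into its result. If the question is settled only after the data are in, it becomes a post-hoc choice in an open-label study of 32 subjects.

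**Working it through.** **Timing, from the flow sheet (cumulative minutes).** First MCC scan 60-124; albuterol 124-130; second scan 130-184; spirometry and coughing 184-204; cough scan 204-208; rest to 418; final scan 418-433. Data needed: Aim 1 by minute 124, Aim 2 by 184, Aim 3 by 208. Between the last outcome scan and completion there remain 433 - 208 = 225 minutes.

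**The plan's own figure.** Section 9.6 raises 10 to 12 per PCD group for 20% dropout: 10 × 1.2 = 12. (Dividing instead, 10/0.8 = 12.5, gives 13; the difference does not matter here.) At 20%, 0.2 × 12 = 2.4 of 12 would drop out.

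**Inputs.** Section 9.6: Ave60Clr healthy 14.3 (SD 7.2), mild 3.6 (SD 2), severe 0.5 (SD 0.25), so the planned mild-severe difference is 3.1. Assumptions, since the documents give no timing: 2 of 12 per PCD group are lost after minute 124, both are replaced, the healthy group stays at 8, and values are normal. Completers-only then analyses 12 per PCD group; keeping valid primary data analyses 14.

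**Precision.**
- Mild mean, 95% half-width t(0.975, n-1) × 2/√n. At n = 12: 2.201 × 0.577 = 1.27. At n = 14: 2.160 × 0.535 = 1.15.
- Mild-severe difference, unequal-variance interval. At 12+12: standard error √((4 + 0.0625)/12) = 0.582, df 11.3, half-width 1.28. At 14+14: 1.16.
- Mild-severe difference, planned Tukey-Kramer interval. At 8/12/12: pooled variance (7 × 51.84 + 11 × 4 + 11 × 0.0625)/29 = 14.05, SD 3.75. Half-width (3.493/√2) × 3.75 × √(2/12) = 3.78. At 8/14/14: pooled SD 3.55, half-width 3.29.

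**Possible shift in the mild-severe difference under completers-only.** For n = 12 normal values, the two lowest are expected at -1.629 and -1.116 SD. Losing them and adding two random replacements moves a group mean by (1.629 + 1.116)/12 = 0.229 SD, which is 0.457 points in the mild group and 0.057 in the severe group.
- Stopping unrelated to clearance: 0.
- Stopping driven by a variable correlated 0.3 to 0.5 with Ave60Clr (the extreme shifts multiplied by the correlation): 0.12 to 0.20 if it acts in the same direction in both groups, 0.15 to 0.26 if in opposite directions.
- Two lowest lost in both groups: 0.457 - 0.057 = 0.40, or 13% of 3.1.
- Lowest lost in mild, highest in severe: 0.457 + 0.057 = 0.51, or 17% of 3.1.
- One lost per group instead of two: 1.629/12 = 0.136 SD, so the two extreme cases give 0.136 × 1.75 = 0.24 and 0.136 × 2.25 = 0.31. The mild half-width is then 1.27 (n = 12) against 1.21 (n = 13).

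The largest shift, 0.51, is 40% of the unequal-variance half-width (0.51/1.28) and about 14% of the planned Tukey-Kramer half-width (0.51/3.78).

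**The case against.** The best reply is that the plan nowhere says that a non-completer's data are thrown away. Section 9.2 describes a database, not an analysis set. Replacement is a recruitment rule, the sentence in section 7.8 can be read as the end of participation, and section 11.6 describes data entry with no completer restriction. A reader might therefore infer either an explicit exclusion or none. The text supports neither fully. It does admit to the database the subjects who follow the protocol, replaces the rest, and links replacement after consent withdrawal to the number analysed; no passage says that partial data are kept. Followed as written, that is a completers-only cohort.

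A second reply is that the consequence is hypothetical: section 9.5 expects no withdrawals, the study lasts one day, and both the losses and their correlation with clearance are assumed. This stands, and it limits the size of the point. A single common cohort for all three aims is also tidier, but that can be kept as a sensitivity analysis.

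A third is that phrases such as following the protocol seem to call for more rules, for instance on coughing in the baseline hour or on missing frames. That goes too far. The text on coughing is "During the first hour of MCC imaging patients will attempt to avoid coughing", so a cough is not clearly a departure, and removing such scans could itself be selective. Section 9.1 describes how the average is built and does not make every 10-minute value a condition of validity. Failed medication withholding already has its own rule in section 6.7: "Subject is noncompliant with the recommended withholding of SABA or ICS/LABA for 12 hours prior to study".

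**Conclusion.** The point holds as a cheap improvement of minor weight. Under sections 9.2, 7.8 and 9.5, subjects with valid outcome data can be displaced by events that have no bearing on those data. On the assumed loss of 2 of 12 per PCD group after minute 124, the cost is a mild-mean half-width of 1.27 instead of 1.15, and a shift in the mild-severe difference of 0 to 0.51 points. The upper end requires that exactly the extreme values be lost, in opposite directions in the two groups. Every shift lies inside the interval for the difference, whether unequal-variance (1.28) or the planned Tukey-Kramer (3.78).

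A reader might infer that the primary comparison is biased or that power is lost. The documents do not support that. They give no timing or cause of loss, the shift is zero if stopping is unrelated to clearance, and replacement holds each PCD group at 12. No changed conclusion is claimed. The healthy group was not examined for its own losses.

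**What to change.** In sections 9.2 and 9.5, state that every eligible subject with the measurements an aim needs is analysed for that aim, regardless of later events and subject to the consent terms:

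- Aim 1: time-zero and 0-60 minute imaging.
- Aim 2 (PCD groups): the same, plus 60-120 minute imaging.
- Aim 3 (PCD groups): the pre-cough and post-cough measurements.

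Replacements add to these subjects and do not displace them. Report non-completers by group with reasons, and give the completers-only result as a sensitivity analysis. No new exclusion for incomplete frames or first-hour coughing is needed.

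The cost is a few sentences. No procedure, visit or stopping criterion changes. The downside is that group sizes may differ slightly between aims, so the single common cohort appears only in the sensitivity analysis. If the sponsor already means to keep partial data, the same sentences put that on record.

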| Statistical Analysis Plans | Aim 1 will provide estimates of the mean and standard deviation of baseline MCC (Ave60Clr) for each group of PCD subjects. The 2 disease groups will be compared to data from healthy subjects using ANOVA followed by multiple comparisons, using the Tukey Kramer correction. Age, gender and the initial deposition C/P will be added as covariates to PCD groups in a linear regression model on MCC. In Aim 2, the change pre- to post-albuterol (Ave120Clr-Ave60Clr) will be calculated for each subject. Estimates of the mean and standard deviations will be reported for each group and compared with paired t-tests. The difference of change between the 2 groups will first be analyzed with an independent t-test. Age, gender and C/P will then be added as covariates in linear regression model. |

| | |
|--|--|
| | 
In Aim 3, the change pre- to post-cough clearance (Ave150Clr-Ave120Clr) will be calculated for each subject. Estimates of the mean and standard deviations will be reported for each group and compared with paired t-tests. The difference of change between the 2 groups will be analyzed with an independent t-test. Age, gender and C/P will then be added as covariates in linear regression model.
 
All tests will be 2-sided, with $\alpha=0.05$. Tests with p values above 0.05 will be considered inconclusive.
 |
|--|--|

2. Introduction: Background and Scientific Rationale

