9.6. Sample Size Rationale

Sample size:

Based on the results of mucociliary transport (MCT) rates (healthy: 6.58 ± 1.39 , *Rspn1*^{-/-}: 1.63 ± 0.78 , other PCD: 0) in our mouse model [13], we expect subjects with a mild genotype to average 25% of the MCC of healthy subjects (healthy: Ave60Clr = $14.3 \pm 7.2\%$; mild expected: $3.6 \pm 2\%$), while subjects with a severe genotype will not show any MCC results, i.e. Ave60Clr not different from 0 (expected 0.5 ± 0.25). With $n=10$, we will be able to observe significant differences between all groups, with $\alpha=0.05$ and power=0.8.

Moreover, we expect the mild genotype group to react to albuterol treatment by doubling their Ave60 Clr, while the group with severe mutations will not. With 10 subjects, we will be able to find a significant response in the mild genotype group with expected Ave60Clr = $7.2 \pm 4\%$. Accounting for 20% possible dropout, we plan to enroll 12 subjects.

10. Safety Monitoring and Management

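### Aim 1's ANOVA with Tukey-Kramer pools SDs of 7.2, 2 and 0.25, so mild versus severe has about 10 to 30% power, not the stated 80%

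*Combined protocol and SAP*

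**What the plan says.** Section 9.3 (Aim 1) compares Ave60Clr across healthy, mild-genotype and severe-genotype subjects: "For this comparison, we will use an ANOVA followed by multiple comparisons, using the Tukey Kramer correction". The synopsis repeats this: "The 2 disease groups will be compared to data from healthy subjects using ANOVA followed by multiple comparisons, using the Tukey Kramer correction". A linear regression follows, with age, gender and initial C/P ratio added to the PCD groups. Section 9.1 plans plots for normality and outliers and does not mention unequal variances. No section names an unequal-variance method.

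Section 9.6 states that with n=10, two-sided alpha 0.05 and power 0.8, "we will be able to observe significant differences between all groups". Its planning values, reading the ± figures as SDs, are healthy 14.3 (7.2), mild 3.6 (2) and severe 0.5 (0.25); the severe group is described as "Ave60Clr not different from 0". Section 9.2 sets the cohort at 12 mild and 12 severe. For the controls it says: "Eight healthy patients will be enrolled and undergo the same MCC protocol to obtain data for comparison".

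**The concern.** The largest planning SD is almost 29 times the smallest (7.2/0.25). ANOVA and Tukey-Kramer in standard form assume a common variance and estimate it from all three groups. The spread among healthy subjects therefore sets the error term for mild versus severe, a comparison in which no healthy subject takes part. For healthy versus PCD the error term is too small, because the most variable group is also the smallest.

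Mild versus severe is the central genotype-phenotype question. The synopsis lists it in the primary objective, and the expected-results text in section 9.3 says "we expect the rate of MCC to be significantly greater in subjects in the “mild genotype” group compared to the PCD patients in the “severe" group. The same text would read a failure to detect a difference as a sign that maintained low-level clearance does not explain the milder phenotype. If the planning values are exactly right, the named test fails to detect the difference about 70% of the time at the enrolled sizes. The study could then report a mechanistic conclusion produced by the choice of error term.

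**Working it through.** **Inputs.** Means, SDs, alpha, power and n=10 are from section 9.6; group sizes 8/12/12 (healthy/mild/severe) from section 9.2; the test from section 9.3. Outcomes are taken as normal, as section 9.1 expects. Planned differences: healthy-mild 10.7, healthy-severe 13.8, mild-severe 3.1.

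**1. Reproducing n=10.** Section 9.6 gives no formula. Take each pair separately, with the larger SD of the pair and alpha 0.05/3: n = 2(2.394 + 0.842)² SD²/Δ², where (2.394 + 0.842)² = 10.47.
- Healthy-mild: 2 × 10.47 × 51.84/114.49 = 9.5, so 10.
- Healthy-severe: 2 × 10.47 × 51.84/190.44 = 5.7, so 6.
- Mild-severe, SD 2: 2 × 10.47 × 4/9.61 = 8.7, so 9.

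The maximum is 10, as stated. This is one route that works; it does not prove which one was used. It requires each pair to be judged on its own SDs.

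**2. Error term of the named test.** Pooled variance = Σ(nᵢ − 1)SDᵢ²/(N − 3).
- 10/10/10: (9 × 51.84 + 9 × 4 + 9 × 0.0625)/27 = 18.63, root 4.32.
- 8/12/12: (7 × 51.84 + 11 × 4 + 11 × 0.0625)/29 = 14.05, root 3.75.

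**3. Smallest significant mild-severe difference.** This is (q/√2) × pooled SD × √(1/n₁ + 1/n₂).
- 10/10/10: 2.479 × 4.317 × √(2/10) = 4.8.
- 8/12/12: 2.470 × 3.749 × √(2/12) = 3.8.

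Both exceed the planned 3.1. At 12/12 the true standard error of this difference is √(4/12 + 0.0625/12) = 0.58; the pooled one is 1.53, or 2.6 times as large.

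**4. The opposite error for healthy-mild.** At 8/12 the true standard error is √(51.84/8 + 4/12) = 2.61; the pooled one is 3.749 × √(1/8 + 1/12) = 1.71, about two thirds of it.

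**5. Simulated power** (200,000 normal data sets per design, 20,000 or more at 30 per group). The Games-Howell statistic is the difference divided by √(s₁²/n₁ + s₂²/n₂), with Welch-Satterthwaite degrees of freedom and critical value q/√2.

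| Healthy/mild/severe n | Tukey-Kramer mild-severe | Tukey-Kramer all three | Games-Howell mild-severe | Games-Howell healthy-mild | Games-Howell all three |
|---|---|---|---|---|---|
| 10/10/10 | about 9.5% | about 9.5% | 96% | 94% | 91% |
| 8/10/10 | 16% | 16% | 96% | 85% | 82% |
| 8/12/12 | 30% | 30% | 99% | 85% | 84–85% |
| 30/30/30 | 83% | 83% | – | – | – |

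Under Tukey-Kramer, healthy-mild (98 to 99%) and healthy-severe (above 99.9%) are rarely missed at the first three sizes, so mild-severe alone limits the chance that all three are significant. Games-Howell healthy-severe power at 8/12/12 is 98%.

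**6. Intervals at 8/12/12.** The mean mild-severe half-width is 3.7 with Tukey-Kramer and 1.5 with Games-Howell. For healthy-mild it is 4.1 and 7.3. The Tukey-Kramer healthy-mild interval covers the true difference 86% of the time, below even the 95% meant to hold for all three pairs jointly.

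**The case against.** The sample-size sum is not wrong. Separate pairwise tests reproduce n=10, so the fault is a mismatch between sections 9.3 and 9.6. That is correct, and it is why the remedy needs no extra participants.

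The follow-on regression may already provide a good mild-severe test. If fitted to PCD subjects only, its power is about 99% (approximation with 3 degrees of freedom lost to covariates). But the text does not say whether healthy subjects are excluded, the model is the adjusted second step, and section 9.6 does not tie its claim to it. If healthy subjects are included, the same pooling problem is likely.

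The loss depends on the healthy SD of 7.2. Assuming 3.5 instead, with the other values unchanged, Tukey-Kramer mild-severe power at 8/12/12 is 92%; assuming 5, it is about 69%. The severe SD of 0.25 is an expectation, not data. This limits how certain the 30% is. However, 7.2 is the plan's own figure, its power claim rests on it, and near-zero clearance in the severe group makes unequal spread likely.

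The aim also reports means and confidence intervals, and the plan calls p above 0.05 inconclusive. That softens the harm, but the expected-results text still draws a conclusion from non-detection.

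Finally, having 8 rather than 10 controls does not cause the mild-severe loss: power is lower at 10/10/10 than at 8/12/12. The control count matters for restating section 9.6 and for healthy-mild power.

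**Conclusion.** The concern holds. On the plan's own means and SDs, the named Aim 1 test has about 9.5% power for mild versus severe at the n=10 of the power statement and 30% at the enrolled 8/12/12, against a stated 80%. About 30 per group would be needed to reach 80% with that test. The healthy-mild interval is too narrow, with 86% coverage at 8/12/12. The cause is the pooled error term, not the number of subjects. This rests on the ± values being SDs, on normal outcomes, on ANOVA and Tukey-Kramer in standard form, and on a healthy SD near 7.2; a much smaller healthy SD would shrink the power loss.

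**What to change.** - In section 9.3 and the synopsis, replace ANOVA with Tukey-Kramer by Welch ANOVA with Games-Howell pairwise tests and simultaneous intervals.
- Restate section 9.6 for 8 healthy, 12 mild and 12 severe and for that test: at the planning values, 99% for mild-severe, about 85% for healthy-mild, 98% for healthy-severe and 84 to 85% for all three pairs. Also show 82% for all three at 8/10/10, the case in which both PCD groups fall to 10, because the margin over 80% is thin.
- State whether the covariate regression includes healthy subjects. Heteroscedasticity-robust (HC3) standard errors are a reasonable choice there; their performance at this size was not calculated here.

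The cost is wording, settled before analysis, with no added participants. Healthy-mild power falls from a nominal 99% to about 85%, and that interval widens from a half-width of about 4.1 to 7.3 points, which is what its coverage requires.
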